3.14 Duration of Follow-Up

Subjects who discontinue IP for any reason other than withdrawal of consent will be followed for AEs for 90 days after the last dose of IP. Subjects who are withdrawn from study for unacceptable

AE(s) will be followed until resolution or stabilization of the AE. Subjects who permanently discontinue IP for reasons other than progression will continue with disease assessments until progressive disease, start of another anti-cancer therapy, withdrawal of consent, death, or end of the study, whichever occurs first.

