6.7 Assessment of Anti-tumor Activity

The primary analysis of anti-tumor activity is according to RECIST v1.1. Tumor size changes will also be assessed in the injected lesion(s) and in the non-injected lesion(s) as available. The same method of assessment and the same technique used to characterize each identified and reported lesion at baseline should be used throughout. Disease assessment will be performed at baseline and at the following intervals until disease progression is confirmed: every 6 weeks through week 54, and every 12 weeks thereafter until year 2, and every 24 weeks until study conclusion. Refer to Section 8 for additional details. Treatment beyond progression is permitted provided the subject meets protocol specified criteria (see Section 8.2). All subjects will be followed for PD unless they withdraw consent.

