7.1 Objective Response Rate

The ORR is defined as the proportion of subjects whose best overall response is a confirmed CR or confirmed PR based on investigator assessment according to RECIST 1.1. The ORR will be estimated with a 95% CI using the exact probability method. The number and percent of subjects with the best overall response of CR, PR, SD, PD and not evaluable (NE) will be summarized. Summary of objective response will be provided for the All Treated population and Response Evaluable population.

The best overall response based on RECIST 1.1 is defined as the best overall response among all post-baseline timepoint assessments until the first PD per RECIST 1.1 or start of new anti-cancer therapy, whichever is earlier. For subjects who have not met the criteria for PD per RECIST 1.1

or have not started a new anti-cancer therapy, the best overall response is defined as the best overall response among all post-baseline timepoint assessments.

Based on the investigator assessment of overall response per RECIST 1.1 at post-baseline assessments, the best overall response will be determined programmatically as the following and

Table 3:

- CR > PR > SD > PD > NE
- CR = at least two determinations of CR with at least 4 weeks apart before progression.
- PR = at least two determinations of PR or better with at least 4 weeks apart before progression (and not qualifying for CR).
- SD = at least one SD or better \geq 35 days after the first dose and before progression (and not qualifying for a CR or PR). The minimum interval from the first dose date for the best response of SD is 6 weeks minus 7 days to allow for visit windows of \pm 7 days (35 days).
- If the minimum interval for SD is not met, the best response will depend on the subsequent assessments. See table 3 for details.
- PD is considered the best overall response when PD is documented and a best overall response of CR, PR, or SD could not be established before documentation of PD. Clinical progression will not be considered as documented disease progression in the determination of the best overall response.
- NE is considered the best overall response when PD has not been documented and a best response of CR, PR or SD could not be established.

Table 3. Best overall response when confirmation of CR and PR required.

Overall response First time point	Overall response Subsequent time point	BEST overall response
CR	CR	CR
CR	PR	SD, PD or PR ^a

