CR	SD	SD provided minimum criteria for SD duration met, otherwise, PD
CR	PD	SD provided minimum criteria for SD duration met, otherwise, PD
CR	NE	SD provided minimum criteria for SD duration met, otherwise, NE
PR	CR	PR
PR	PR	PR
PR	SD	SD, provided minimum criteria for SD duration met, otherwise, PD
PR	PD	SD provided minimum criteria for SD duration met, otherwise, PD
PR	NE	SD provided minimum criteria for SD duration met, otherwise, NE

Overall response First time point	Overall response Subsequent time point	BEST overall response
NE	NE	NE

The best percent change from baseline in target lesion sum of diameters is defined as the largest reduction or smallest increase (in the case where a reduction does not occur) from baseline observed over all post-baseline disease assessments and will be presented using a waterfall plot.

Target lesion, non-target lesion, new lesion and response assessments will be presented in data listings. The percent change from baseline/nadir in target lesion sum of diameters will be kept 2 decimal places (xx.xx%) in the data listing and rounding is not required.

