7.3 Duration of Response

The DOR is defined as the time from the date of the first CR or PR (confirmed at least 28 days later) to the date of first documented disease progression per RECIST 1.1 or death, whichever occurs first. Only subjects who have achieved a confirmed CR or confirmed PR will be evaluated for DOR. If a disease progression does not occur, DOR will be censored as of the date of the last evaluable disease assessment. The evaluable disease assessment is defined as an assessment for which the overall response can be determined. DOR will be summarized descriptively and graphically using Kaplan-Meier methods if data warrants. Individual DOR will be presented in a data listing.

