7.4 Progression Free Survival

The PFS is defined as time from the first day of treatment to the first documented disease progression per RECIST 1.1 or death, whichever occurs first. Subjects who have not progressed at the time of analysis will be censored at the latest date of assessment from their last evaluable disease assessment. The censoring guidance and the date of PD/death or censoring are given in the

Table 4. PFS will be summarized using Kaplan-Meier method if data warrants. Individual PFS will be listed for the All Treated population.

Table 4. Summary of Censoring Guidelines for PFS based on RECIST1.1

Situation	Date of PD/Death or Censoring	PFS Outcome
Documented PD or death	Date of the PD or death, whichever comes first	Event (unless the censoring rule specified below)
Death or PD immediately after ≥ 2 consecutive missed or non-evaluable disease assessments ¹ as per the protocol specified assessment schedule	Date of last evaluable disease assessment prior to missed or non-evaluable assessments, or the first dose of investigational product, whichever occurred last	Censored
No PD or death at time of analysis or lost to follow-up	Date of last evaluable disease assessment	Censored
No baseline disease assessment OR no post-baseline disease assessment AND no death prior to second scheduled post-baseline disease assessment	Date of first dose	Censored

¹ Two or more consecutive disease assessments is defined as $\geq 16+1$ weeks for the first 6 months or $\geq 24+1$ weeks for 6-24 months (two disease assessments as per protocol plus a one week visit window) after the last evaluable post-baseline disease assessment. If a subject has two or more consecutive missed or non-evaluable assessments followed by an assessment showing no radiologic disease progression, then the assumption will be that the subject did not progress during the missed or non-evaluable assessments.

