7.5 Change from Baseline for Injected and Non-injected Lesions

Change from baseline diameter for each individual injected and non-injected lesion will be provided in a data listing. The best percent change from baseline for each individual injected and non-injected lesion will be presented using a waterfall plot.

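### The waterfall plots lack the cut at new anti-cancer therapy that SAP 7.1 applies to best response, and the PFS/DOR convention is unstated (minor)

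*SAP*

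**What the plan says.** SAP 7.1 determines best overall response from post-baseline assessments "until the first PD per RECIST 1.1 or start of new anti-cancer therapy, whichever is earlier". Later in the same section, the best percent change in the target-lesion sum is the deepest fall (or the least growth, where nothing shrinks) "from baseline observed over all post-baseline disease assessments and will be presented using a waterfall plot". SAP 7.5 adds the lesion-level plot and states no window: "The best percent change from baseline for each individual injected and non-injected lesion will be presented using a waterfall plot". These become Figures 14.2.2 and 14.2.3.

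For DOR, SAP 7.3 says: "If a disease progression does not occur, DOR will be censored as of the date of the last evaluable disease assessment". For PFS, SAP 7.4 says: "Subjects who have not progressed at the time of analysis will be censored at the latest date of assessment from their last evaluable disease assessment". In Table 4, the first row dates the event at "Date of the PD or death, whichever comes first". Neither section mentions new anti-cancer therapy.

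On collection, protocol 3.14 has subjects who stop drug for reasons other than progression "continue with disease assessments until progressive disease, start of another anti-cancer therapy, withdrawal of consent, death, or end of the study". SOA footnote j, protocol sections 8 and 8.1, and SAP 3.5 and the opening of SAP 7 also stop at new therapy. Protocol 6.7 differs: "All subjects will be followed for PD unless they withdraw consent".

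**The concern.** The response table and the two waterfall plots describe the same subjects under different windows. A scan taken after another cancer drug has started cannot improve best overall response, but it can set the waterfall bar. A subject shown as SD in Table 14.2.1 could then have a deep bar in Figure 14.2.2 or 14.2.3 produced by the other drug, and nothing in the SAP would explain the mismatch. Change in injected and non-injected lesions is a stated secondary outcome, and clinical activity is part of the evidence for the RP2D, so the plots should show SL-172154 alone.

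For PFS and DOR the gap is an unstated convention. The SAP does not say whether progression or death after a new drug counts as an event, or whether the subject is censored when that drug starts.

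**Working it through.** **The plan's one related number.** The Table 4 footnote sets two missed assessments at 16 + 1 = 17 weeks in the first 6 months. On the 6-weekly schedule, two intervals plus the window give 2 × 6 + 1 = 13 weeks; 17 would fit an 8-week interval (2 × 8 + 1). The figure does not reproduce from the schedule. That is a separate inconsistency. It matters here only because it limits how late a death can still be a PFS event.

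**The rules side by side**

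| Quantity | Source | Rule | New therapy named? |
|---|---|---|---|
| Best overall response, ORR | SAP 7.1 | up to first PD or new therapy | yes |
| TTR; entry into DOR | SAP 7.2, 7.3 | need a confirmed response, so should inherit the 7.1 cut | not directly |
| Target-sum waterfall | SAP 7.1, Figure 14.2.2 | all post-baseline assessments | no |
| Per-lesion waterfall | SAP 7.5, Figure 14.2.3 | no window | no |
| End of DOR | SAP 7.3 | PD or death, otherwise last evaluable assessment | no |
| PFS | SAP 7.4, Table 4 | four situations | no |

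**Would an off-schedule scan reach the plots?** Yes, if it is recorded. SAP 5.2 lets unscheduled data into maximum and minimum values over time, and a best percent change is a minimum over time.

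**Effect on one bar (assumed subject).** Baseline sum 60 mm; 57 and 54 mm at two scheduled scans on study (say weeks 6 and 12); then a new drug; then 30 mm on a later recorded scan. Percent change = 100 × (sum - 60)/60.
- 57 mm: -5%
- 54 mm: -10%
- 30 mm: -50%

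Best overall response uses only the first two scans. Neither reaches the 30% fall needed for PR, so it is SD. The bar is -50% under the present wording and -10% with the 7.1 cut. At the planned 18 subjects, one subject is 1/18 = 5.6% of the bars in Figure 14.2.2; with fewer subjects the share is larger.

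**PFS and DOR (assumed responder).** First PR at week 6, last scan and new drug at week 18, no PD, death at week 28. The gap from last scan to death is 28 - 18 = 10 weeks, inside both 17 and 13 weeks, so Table 4 counts an event. By SAP 5.3.3, months = (days + 1)/30.4375.
- PFS: event at (28 × 7 + 1)/30.4375 = 6.5 months; with a cut at new therapy, censored at (18 × 7 + 1)/30.4375 = 4.2 months.
- DOR: event at (22 × 7 + 1)/30.4375 = 5.1 months; with the cut, censored at (12 × 7 + 1)/30.4375 = 2.8 months.

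DOR has no missed-assessment limit, so a later death would still count there.

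**Direction.** The recorded time is longer without the cut, but the cut also removes an event. If that death were the only event among 18 otherwise fully followed subjects, Kaplan-Meier PFS after week 28 would be 17/18 = 94.4% with the death counted and 100% with it censored.

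**The case against.** The strongest reply is that the plan hardly generates such scans. SAP 3.5 and the opening of SAP 7, which governs 7.1 to 7.5, end disease assessments at new therapy for subjects who stop drug before progression. Protocol 3.14, footnote j, 8 and 8.1 agree. The sentence in protocol 6.7 stands nearly alone, and 6.7 itself sends the reader to section 8, which contains the stop. Protocol 3.6.1 bars other anti-cancer drugs during SL-172154. Listings of lesions and responses would also let a careful reader trace a late scan behind a bar.

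Most of this stands. A reader might infer that the plan routinely collects tumor data on the next drug; the documents do not support that. But a collection instruction does not tell the programmer what to do with a scan already in the database. SAP 7.1 applies an explicit cut to best response despite the same collection stop, so the case was foreseen for the table and left open for the figures.

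A reader might also infer that PFS and DOR are biased in favor of SL-172154. That is not supported either. PFS is defined as time to progression or death, and counting the event whatever therapy follows is consistent with that definition. Censoring at new therapy is a different estimand choice, may be informative, and can remove events. Nor is the death in the example sure to be recorded: protocol 7 limits recording to AEs and SAEs before the new agent, and AE follow-up ends 90 days after the last dose. I found no scheduled survival follow-up described, though SAP 5.3.1 mentions it in passing.

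**Conclusion.** The point holds as a minor one. The mismatch between the 7.1 response window and the two waterfall windows is plain on the text, and any scan recorded after a new drug would be plotted under one rule and excluded under the other. The -50% against -10% contrast is an assumed case, not an estimate. The documents do not give the number of affected subjects. It is probably small, because most passages stop scans at new therapy and SAP 1 records that enrollment closed early.

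For PFS and DOR the finding is only that the convention is missing. PFS is exploratory, Kaplan-Meier summaries are conditional on the data, and the planned outputs contain no PFS or DOR table or curve, only Listings 16.2.6.5 and 16.2.6.6.

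The target-sum waterfall also has no cut at first progression. I leave that aside: protocol 8.2 allows SL-172154 beyond progression, so later shrinkage need not come from another drug.

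**What to change.** 1. In SAP 7.1 and 7.5, limit the best percent change of the target sum, and of each injected or non-injected lesion, to assessments on or before the start of new anti-cancer therapy. Say so in the footnotes of Figures 14.2.2 and 14.2.3.
2. In Table 4 and SAP 7.3, state how new therapy before PD or death is handled, whether by censoring or by counting the later event, and flag the affected subjects in Listings 16.2.6.5 and 16.2.6.6.
3. Reconcile protocol 6.7 with 3.14, footnote j and section 8 on when disease assessments end.

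The cost is a few sentences and one filter on a date that 7.1 already requires. It should be settled before Database Freeze, the point by which the SAP says its analysis decisions are made. The first change loses no information on SL-172154 alone, and the listings still show every recorded scan. If censoring is chosen under the second, some follow-up is given up, possibly informatively, and the report should say so.

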7.2 Time to Response

The TTR is defined as the time from the first dose until the first documentation of a subsequently confirmed objective response (confirmed CR or confirmed PR) based on RECIST 1.1. Only subjects who have achieved confirmed objective response will be evaluated for TTR. TTR will be summarized descriptively and graphically using Kaplan-Meier methods if data warrants. Individual TTR will be presented in a data listing.

7.3 Duration of Response

The DOR is defined as the time from the date of the first CR or PR (confirmed at least 28 days later) to the date of first documented disease progression per RECIST 1.1 or death, whichever occurs first. Only subjects who have achieved a confirmed CR or confirmed PR will be evaluated for DOR. If a disease progression does not occur, DOR will be censored as of the date of the last evaluable disease assessment. The evaluable disease assessment is defined as an assessment for which the overall response can be determined. DOR will be summarized descriptively and graphically using Kaplan-Meier methods if data warrants. Individual DOR will be presented in a data listing.

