2. STUDY OBJECTIVES AND OUTCOME MEASURES

Objective	Outcome Measure
Primary Objectives	
To evaluate the safety and tolerability of ITI administration of SL-172154 and to identify the maximum tolerated dose (MTD) or maximum administered dose (MAD) of SL-172154
 
Safety/tolerability outcomes include: incidence of all adverse events (AEs) and immune-related adverse events (irAE), serious adverse events (SAEs), fatal SAEs, dose limiting toxicity (DLT), AEs and irAEs leading to discontinuation, and changes in safety assessments (e.g., laboratory parameters, vital signs etc.) per National Cancer Institute Common Terminology Criteria for Adverse Events (NCI-CTCAE – version 5.0).
 
The MTD is defined based on the rate of DLTs and the MAD is the highest dose administered.

Secondary Objectives	
To select the recommended Phase 2 dose (RP2D) for SL-172154 when administered by intratumoral injection (ITI)
 
Based on review of all data collected during dose escalation and the pharmacodynamic cohort including safety, tolerability, PK, anti-tumor activity, and pharmacodynamic effects
 
To assess preliminary evidence of anti-tumor activity of SL-172154 when administered by ITI
 
Response per investigator assessment according to Response Evaluation Criteria in Solid Tumors version 1.1 (RECIST v1.1).
 
 ▪ Objective response rate (ORR) (proportion of subjects whose best response is a complete response [CR] or partial response [PR]) ▪ Time to response (TTR): time from the first dose until the first response (CR or PR, whichever is recorded first) that is subsequently confirmed ▪ Duration of response (DOR): time between first response (CR or PR, whichever is recorded first) that is subsequently confirmed and date of disease progression ▪ Change from baseline lesion diameter for injected lesion ▪ Change from baseline lesion diameter for non-injected lesion

Objective	Outcome Measure
Secondary Objectives	
To evaluate anti-drug antibodies (ADA) to SL-172154 when administered by ITI during and after treatment.	
 ▪ Number/proportion of subjects with positive ADA titer ▪ ADA duration ▪ Transient vs. persistent ADA

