2. STUDY OBJECTIVES AND OUTCOME MEASURES

Objective	Outcome Measure
Primary Objectives	
To evaluate the safety and tolerability of ITI administration of SL-172154 and to identify the maximum tolerated dose (MTD) or maximum administered dose (MAD) of SL-172154	
Safety/tolerability outcomes include: incidence of all adverse events (AEs) and immune-related adverse events (irAE), serious adverse events (SAEs), fatal SAEs, dose limiting toxicity (DLT), AEs and irAEs leading to discontinuation, and changes in safety assessments (e.g., laboratory parameters, vital signs etc.) per National Cancer Institute Common Terminology Criteria for Adverse Events (NCI-CTCAE – version 5.0).
 
The MTD is defined based on the rate of DLTs and the MAD is the highest dose administered.

Secondary Objectives	
To select the recommended Phase 2 dose (RP2D) for SL-172154 when administered by intratumoral injection (ITI)	Based on review of all data collected during dose escalation and the pharmacodynamic cohort including safety, tolerability, PK, anti-tumor activity, and pharmacodynamic effects.
To assess preliminary evidence of anti-tumor activity of SL-172154 when administered by ITI	Response per investigator assessment according to Response Evaluation Criteria in Solid Tumors version 1.1 (RECIST v1.1).

	
 ▪ Objective response rate (ORR) (proportion of subjects whose best response is a complete response [CR] or partial response [PR]) ▪ Time to response (TTR): time from the first dose until the first response (CR or PR, whichever is recorded first) that is subsequently confirmed ▪ Duration of response (DOR): time between first response (CR or PR, whichever is recorded first) that is subsequently confirmed and date of disease progression ▪ Change from baseline lesion diameter for injected lesion ▪ Change from baseline lesion diameter for non-injected lesion
To evaluate anti-drug antibodies (ADA) to SL-172154 when administered by ITI during and after treatment.	
 ▪ Number/proportion of subjects with positive ADA titer ▪ ADA duration ▪ Transient vs. persistent ADA

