5.3 Data Handling

5.3.1 Premature Withdrawal and Missing Data

Subjects who prematurely withdraw from the study will be included in analyses up to the time of withdrawal, regardless of the duration of treatment and survival follow-up.

Missing data occurs when any requested data is not provided, leading to blank field on the collection instrument. These data will be indicated using a “blank” in subject data listings. Answers such as “Not applicable” and “Not evaluable” are not considered to be missing data and should be displayed as such.

Subjects with unknown or missing best response will be assumed to be non-responders and will be included in the denominator when calculating percentages. Subjects with the designation of treatment relationship for adverse events (AEs) and serious adverse events (SAEs) missing will have the worst case assumed to impute the relationship: if the relationship to study treatment is missing, it will be assumed to be “Yes” for summary of drug-related AE or SAE.

For the time to event endpoints including DOR and PFS, the missing data handling method will be censoring. Censoring mechanisms for these endpoints are described in section **Error! Reference source not found..**

The length of study treatment for each subject will depend on the safety, tolerability, and efficacy of the treatment, so the duration of treatment will vary across subjects. Subjects with shorter duration of treatment due to the natural history of their disease or medical necessities of treatment of their disease will not be considered to have missing data.

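### SAP 7.3 contradicts itself on whether a responder's death without documented progression is an event or a censored time for duration of response

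*SAP*

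**What the plan says.** SAP 7.3 opens by running DOR from the first confirmed response "to the date of first documented disease progression per RECIST 1.1 or death, whichever occurs first". Its second sentence limits the analysis to confirmed responders. Its third is the censoring rule: "If a disease progression does not occur, DOR will be censored as of the date of the last evaluable disease assessment". That rule makes no exception for death.

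The objectives table in SAP Section 2 has a different end point: "Duration of response (DOR): time between first response (CR or PR, whichever is recorded first) that is subsequently confirmed and date of disease progression". The protocol synopsis and protocol Section 2 likewise end DOR at progression ("that is subsequently confirmed and date of disease progression"). None of these three lines names death.

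On censoring in general, SAP 5.3.1 says: "For the time to event endpoints including DOR and PFS, the missing data handling method will be censoring". It then refers the reader to a section for the details, but the reference is a broken link. The only censoring table, Table 4 in SAP 7.4, is titled for PFS.

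On the analysis itself, protocol 9.2.5 plans Kaplan-Meier for DOR among confirmed responders. SAP 7.3 makes this conditional: "DOR will be summarized descriptively and graphically using Kaplan-Meier methods if data warrants". The SAP appendix names one DOR output, Listing 16.2.6.5.

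**The concern.** DOR is a secondary outcome measure, and every responder needs one end date and one status, even in a listing. For a responder who dies without documented progression, two sentences of the same section give different dates and different statuses, and no order of precedence is stated. The choice is left to whoever programs the endpoint.

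If the censoring sentence wins, a death is treated as if the response might have continued. Such censoring is informative, and it usually raises the Kaplan-Meier curve relative to the definition at the head of the section. The same death would normally count as an event for PFS, so the two endpoints would treat one subject differently without explanation.

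**Working it through.** The plan gives no figure for DOR, so there is nothing to reproduce. The check is a comparison of texts, followed by Kaplan-Meier arithmetic on assumed data.

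**Step 1: what each sentence of SAP 7.3 does with a confirmed responder.**

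| Situation | Defining sentence | Censoring sentence |
|---|---|---|
| Progression documented, with or without later death | Event at progression | Not censored |
| Neither progression nor death | No event | Censored at last evaluable assessment |
| Death, no documented progression | Event at death | Censored at last evaluable assessment |

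Only the third row conflicts.

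**Step 2: whether another text settles that row.** The PFS text in SAP 7.4 is just as loose: "Subjects who have not progressed at the time of analysis will be censored at the latest date of assessment from their last evaluable disease assessment". Table 4 then resolves it, because death is listed as an event and the row for censored subjects reads "No PD or death at time of analysis or lost to follow-up". DOR has no such table, and the pointer in SAP 5.3.1 leads nowhere. The Section 2 lines favour the censoring sentence, while the opening of 7.3 goes against it.

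**Step 3: size in a small example.** Assumed data, in months from first response: progression at 4; death without progression at 6, last scan at 5.5; one response ongoing at 9. The estimate is S(t) = product over event times of (1 − d/n), where d is the number of events and n the number at risk.

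- Death as an event: S(4) = 1 − 1/3 = 0.667; S(6) = 0.667 × (1 − 1/2) = 0.333. The median is 6 months.
- Death censored at 5.5: S(4) = 0.667, with no later event. The median is not reached.
- Listed duration for the subject who died: 6 months (event) or 5.5 months (censored). The listed value gets shorter, not longer.

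**Step 4: the direction is not guaranteed.** Assumed data, in weeks: progression at 24; death at 26 with last evaluable scan at 18, so that the week-24 scan was missed; progression at 30.

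- Death as an event: S(24) = 2/3 = 0.667, S(26) = 0.333, S(30) = 0. The median is 26.
- Death censored at 18: two remain at risk, so S(24) = 1/2 = 0.5 and S(30) = 0. The median is 24 if taken as the first time the curve is at or below 0.5. A convention that averages across a flat step at exactly 0.5 would give (24 + 30)/2 = 27.

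The reversal of the median therefore depends on that convention. Between weeks 24 and 26 the curve itself is lower under censoring (0.5 against 0.667) whatever the convention.

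**Step 5: average size under stated assumptions.** A simulation took exponential DOR with a true median of 26 weeks, scans every 6 weeks with none missed, and 52 weeks of follow-up. Deaths without progression made up 5% to 30% of the event hazard. Only the 6-week interval comes from the documents. Large-sample results:

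| Share of deaths | S at 26 weeks, event / censored | Median in weeks, event / censored |
|---|---|---|
| 5% | 0.526 / 0.545 | 30 / 30 |
| 10% | 0.523 / 0.560 | 30 / 30 |
| 20% | 0.521 / 0.599 | 30 / 36 |
| 30% | 0.518 / 0.639 | 30 / 42 |

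With 2 to 5 responders, censoring raised the median in about 8% to 19% of simulated trials at a 10% share of deaths, and in about 25% to 49% at a 30% share. In the rest it was unchanged; it was never lower when no scan was missed.

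**The case against.** The defining sentence already makes death an event, and the SAP uses the same shorthand for PFS, where Table 4 shows that death counts. SAP 5.3.1 treats the two endpoints together. A sensible programmer would probably count the death, and the censoring sentence may lack only a phrase. This makes death-as-event the more natural reading. It does not settle the matter, because Table 4 is confined to PFS and three other DOR lines stop at progression.

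The consequences may also be slight. Enrollment stopped early, the planned size was only about 18, Kaplan-Meier is conditional, and the appendix lists no DOR table or curve. Deaths have their own listing (16.2.7.4), so they remain visible. All of this stands, and it limits the impact. Against the progression-only definition in the protocol and SAP Section 2, censoring such a death is not even a departure; the overstatement exists only relative to SAP 7.3. Finally, the documents give no response rate or death rate, so every number above is illustrative.

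**Conclusion.** The contradiction is real and unresolved, but narrow: it affects only confirmed responders who die without documented progression.

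A reader might infer that the plan censors responders who die and therefore overstates DOR. The documents do not support that. The text conflicts with itself rather than choosing censoring, and a responder who progresses before dying is an event under both sentences. Overstatement needs three things: the censoring sentence taken literally, at least one such death, and a Kaplan-Meier summary. Even then a missed scan can lower part of the curve, and the listed individual duration becomes shorter and marked censored.

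Where those conditions hold, the usual direction is upward. In the assumed three-responder case the median goes from 6 months to not reached; under the simulation assumptions, the 26-week estimate rises by 0.019 (0.545 − 0.526) to 0.121 (0.639 − 0.518). With no such death the two rules give identical results. The correction is worth making because it removes a choice that should be settled before the data are frozen, not because a large bias has been shown.

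**What to change.** Make these changes in the SAP:

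- In 7.3, replace the opening condition of the censoring sentence with *If neither disease progression nor death occurs*, and leave the rest as it is.
- In Section 2, add *or death* to the DOR line.
- Note that counting death adds to the protocol's definition. Protocol 9.2 allows additions to be documented in the SAP and final study report.
- Repair the cross-reference in 5.3.1.
- State whether the Table 4 rule, which censors a death that follows two or more missed or non-evaluable assessments, also applies to DOR. Without this, DOR and PFS could still treat the same death differently.

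The cost is SAP wording, with no new data. Changing the DOR lines in the protocol would mean an amendment with IRB/IEC review (protocol 13.2), and is not needed.
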